#### 7.4 Randomisation

Young people will be randomised in 1:1 ratio to either BA, psychoeducation and TAU or psychoeducation and TAU using stratified block randomisation. Randomisation will be implemented using a web-based system designed and developed by the data management team at York Trials Unit (YTU). The allocation sequence will be generated by a YTU statistician and embedded into the randomisation system. Randomisation will be stratified by site and use randomly-varying blocks of randomly-varying sizes. The Trial Managers based at YTU will inform the behavioural activation therapists who has been allocated to receive behavioural activation.

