# 9.2 Statistical Analysis

Analyses will be conducted in Stata version 17 (or later) following intention-to-treat principles and will follow a detailed pre-specified statistical analysis plan. Statistical

significance will be assessed at the 5% level unless otherwise stated, and 95% confidence intervals will be provided as appropriate. Analyses and results will be reported according to CONSORT guidelines. The flow of individuals through the trial will be reported in a CONSORT diagram, including the number screened (and reasons for ineligibility) and approached for consent (and reasons for non-consent), the number randomised, adherence to allocated treatment, follow-up data completeness and the number of participants included in the primary analysis. Descriptive summaries of continuous data by trial arm will be given in terms of the mean and standard deviation (or median and inter quartile range as appropriate). Descriptive summaries of categorical data will be given in terms of frequencies and proportions. No formal statistical testing will be conducted at baseline. Information on intervention delivery including number and duration of sessions will be summarised descriptively.

The primary outcome (total MFQ-C score) will be summarised descriptively at each time point and analysed using a mixed-effects linear regression model, including all available time points. The model will include trial arm, time, arm-by-time interaction, baseline MFQ score and other important baseline variables as fixed effects. Random effects will be included to account for the repeated measures within patients and for possible clustering by therapist (nested within treatment arm). The primary analysis will compare the groups at 6-months post-randomisation. Secondary analyses will compare the groups at 12-weeks and 12-months post-randomisation. Different covariance patterns for the repeated measurements will be explored and the most appropriate pattern will be used for the final model. Data will be assumed missing at random. Secondary outcomes will be analysed using similar models as described above (with binary outcomes being analysed using a mixed-effects logistic regression model), adjusting for the same fixed and random effects.

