# 11.1 Cost-Utility & Cost-Effectiveness: trial-based analysis

The cost to train the BAY therapists and the cost of their time to deliver the intervention therapy sessions will be estimated as the intervention cost. This will be added to the cost of health and social care resources used by YP in the intervention arm to generate an overall cost for that treatment group. For the TAU+PE group, their overall cost will be generated from their use of health and social resources only. The primary analysis will take the health and social care perspective and so will only include these costs. A secondary analysis will include the cost of 'lost productivity' for parents/carers during the time they spend with YP at (and travelling to) healthcare contacts. Unit costs will be derived from published sources (e.g. NHS Schedule of Reference Costs; PSSRU Unit Costs of Health and Social Care) using the most up-to-date versions at the time of the analysis.

The measure of health benefit in the primary analysis will be YP's QALYs derived from the CHU-9D at baseline and 6-month follow-up. A secondary analysis will derive YP's QALYs from the EQ-5D-Y at these timepoints. QALYs will be estimated using an area under the curve approach.

The difference in costs between the treatment groups will be calculated using a glm regression model with log link and gamma family to account for the typically skewed nature of cost data. The difference in QALYs between the groups will be estimated using a linear regression model. Both regression models will include key covariates, as specified in the statistical analysis. An incremental cost-effectiveness ratio (ICER) will be calculated by dividing the difference in costs by the difference in QALYs between the treatment groups. This will be reported as a cost per QALY. Non-parametric bootstrapping will be used to produce a cost-effectiveness plane to demonstrate uncertainty in the results. A cost-effectiveness acceptability curve (CEAC) will also be generated to illustrate the probability that either treatment is cost-effective at a range of willingness to pay (WTP) thresholds.

The health utility of parents/carers during the study period will be derived from the EQ-5D-5L and compared between the treatment groups.

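### As written, section 9.2 adjusts secondary outcomes for baseline MFQ and not for their own baseline, giving up precision the trial has already collected the data for

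*Protocol*

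**What the plan says.** Section 9.2 describes the primary model for MFQ-C: "The model will include trial arm, time, arm-by-time interaction, baseline MFQ score and other important baseline variables as fixed effects". Random effects cover repeated measures within patients and therapist clustering within arm. For the other outcomes the section says "Secondary outcomes will be analysed using similar models as described above", with logistic models for binary outcomes, and closes the sentence with "adjusting for the same fixed and random effects".

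Three other places bear on the covariate lists:

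- Section 7.4: "Randomisation will be stratified by site". Site is not named in the model in 9.2, but the list there ends with an open class of further baseline variables.
- Section 11.1, on costs and QALYs: "Both regression models will include key covariates, as specified in the statistical analysis". The QALYs are "derived from the CHU-9D at baseline and 6-month follow-up", by area under the curve.
- Sections 9.2 and 11 defer detail to a statistical analysis plan and a health economics analysis plan respectively. Neither is shown.

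**The concern.** The best single predictor of a follow-up questionnaire score is usually the same questionnaire at baseline. The primary outcome gets this: MFQ-C is adjusted for baseline MFQ. The clause on secondary outcomes then carries the same fixed effects across, and the only outcome-specific term among them is baseline MFQ. Taken at its word, the RCADS model would contain baseline MFQ but not baseline RCADS. The carer PHQ-9 model would contain the young person's depression score but not the carer's own baseline.

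This differs from a covariate list left for the analysis plan to complete. The sentence states a rule, and an analysis plan that swapped in each outcome's own baseline would depart from the protocol's wording. What is at stake is precision on the secondary outcomes. Randomisation protects those comparisons from systematic bias, but with the weaker covariate the intervals are wider and chance baseline differences are less fully corrected.

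**Working it through.** **Which outcomes have a baseline.** Table 1 schedules these at baseline and at follow-up: SDQ (young person and parent), RCADS, BADS, goal score, parent MFQ, and carer PHQ-9 and GAD-7. (The shorter list in section 7.3 omits the BADS; Table 1 includes it.) The Aspects of Care checklist starts at 12 weeks and has no baseline.

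**The plan's own figure first.** The revised inputs in section 9.1 are effect size 0.30, baseline-follow-up correlation 0.45, ICC 0.01 in the intervention arm, groups of 12, 70% retention and 80% power (two-sided 5% assumed):

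- n per arm = ((1.960 + 0.842)/0.30)² × (1 − 0.45²) × (2 + 11 × 0.01) = 87.2 × 0.7975 × 2.11 = 146.8
- Rounded up to whole groups: 13 × 12 = 156
- 156/0.70 = 222.9, so 223 per arm and 446 in total

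The stated 446 reproduces. It relies on MFQ-C being adjusted for its own baseline, which the primary model does, so it does not change here.

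**Loss for a continuous secondary outcome.** With a covariate that correlates r with follow-up, residual variance is proportional to 1 − r². The protocol gives no correlations for these outcomes. Assume 0.45 with own baseline (borrowed from MFQ-C) and 0.2 to 0.3 with baseline MFQ:

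| | own baseline, r = 0.45 | baseline MFQ, r = 0.3 | baseline MFQ, r = 0.2 |
|---|---|---|---|
| 1 − r² | 0.7975 | 0.91 | 0.96 |
| variance relative to own baseline | 1 | 1.14 | 1.20 |
| SE saved by own-baseline adjustment | – | 1 − √(0.7975/0.91) = 6% | 1 − √(0.7975/0.96) = 9% |
| n per arm for 80% power, d = 0.30, before rounding to groups | 147 | 168 | 177 |
| power at 156 per arm, d = 0.30 | 82% | 77% | 75% |

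The power row uses SE = √((1 − r²) × 2.11/156), which gives 0.104, 0.111 and 0.114. It is an illustration only, because the trial is not powered for secondary outcomes.

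**A second set of assumptions.** Let baseline MFQ predict the outcome only through that outcome's own baseline, with a correlation of 0.3 to 0.7 between the two baselines. Then r for baseline MFQ is 0.45 × 0.3 = 0.135 up to 0.45 × 0.7 = 0.315. Residual variance is 23% down to 13% larger than with own-baseline adjustment. The order of magnitude is the same.

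**QALYs, for the confirmation in 11.1.** Over six months the area is 0.5 × (u₀ + u₆)/2 = 0.25u₀ + 0.25u₆, so baseline utility is part of the outcome with weight 0.25. An assumed arm difference of 0.01 to 0.03 in baseline utility adds 0.0025 to 0.0075 QALY directly if nothing in the model adjusts for it.

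**The case against.** The strongest reply is that 9.2 speaks of similar models, which implies adaptation. A strictly literal reading cannot be carried out for every outcome: in Table 1 the carer PHQ-9 and GAD-7 have a single follow-up, at 6 months, so time and arm-by-time terms cannot carry over to them. If some adaptation is unavoidable, replacing baseline MFQ with each outcome's own baseline is a natural part of it. This stands as a reason to call the wording badly fixed and not to conclude that the analysis will be wrong. It does not remove the point, because the clause that specifies the covariates says they are the same.

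Three stronger readings are tempting, and the document does not support them:

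- **That site is left out of the model and power suffers.** The list in 9.2, "baseline MFQ score and other important baseline variables as fixed effects", is open and does not exclude site; completing it is ordinary work for the analysis plan. The consequence is also modest. In simulations at the planned size (2,500 runs per setting), power without a site term was 78, 77 and 73% with 0, 2 and 5% of variance assumed between sites, and 78, 80 and 82% with it. A second run gave 80, 80 and 75% without and 80, 82 and 83% with. Between 0 and 2%, the change without site is within Monte Carlo error (about 0.8 points per estimate). Where there is an effect, the standard error is too large; no bias is shown.
- **That costs and QALYs inherit the primary covariates unchanged.** Section 11.1 refers to key covariates from the statistical analysis, which may mean 9.2 or the analysis plan, and a health economics analysis plan is promised. Baseline utility and baseline cost are not named, but neither are they excluded. The QALY shift shown above is for a comparison with no adjustment; a model containing baseline MFQ would absorb part of it.
- **That every secondary outcome is affected.** Outcomes without a baseline, such as Aspects of Care or discharge from the service, cannot be adjusted for one.

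**Conclusion.** The point holds for secondary outcomes that are measured at baseline. As written, 9.2 gives them baseline MFQ and not their own baseline. The loss is one of precision: 14 to 20% in participants' worth of information, or 6 to 9% in the standard error, for continuous outcomes under the assumed correlations (0.45 with own baseline, 0.2 to 0.3 with baseline MFQ). The alternative assumptions give 13 to 23% in residual variance. A measure whose own-baseline correlation is closer to its correlation with baseline MFQ would lose less.

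The primary analysis is correctly adjusted, and no stated sample size or power figure changes. Naming site, baseline utility and baseline cost is worth doing in the same edit, but as confirmation of what open lists may already intend. This is a free improvement, not an error that threatens the trial's conclusion.

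**What to change.** In section 9.2, replace the closing clause on secondary outcomes with: *adjusting for the outcome's own baseline value where one is measured, in place of baseline MFQ, and otherwise using the primary model's fixed and random effects*. The condition is needed for outcomes that have no baseline.

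In the same amendment, as confirmations:

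- name site, the randomisation stratum, as a fixed effect in 9.2;
- state in 11.1 that the QALY model includes baseline utility and the cost model includes baseline service-use cost.

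The cost is wording in the protocol, with the analysis plans brought into line. No new data are needed: Table 1 already schedules the questionnaires, CHU-9D, EQ-5D-Y and service-use schedule at baseline. Five sites use four degrees of freedom.

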# **10. QUALITATIVE STUDY**

# 10.1. Study design

An embedded qualitative study will capture and compare the experiences of young people and professionals participating in the RCT as a means of assessing BA's acceptability, but also as a way of understanding some of the contextual, implementation and mechanistic factors that may influence intervention use and outcomes.

# 10.2. Participants and sample size

# Young people and Carers

During the internal pilot, we will seek to identify and recruit 15 'early exit' participants who initially consent but who do not commence the BAY intervention. These young people and/or their designated carer (where available) will be invited to participate in a qualitative interview to explore potential barriers and enablers to intervention commencement.

Across the internal pilot and main trial phases, we will complete one-to-one qualitative interviews with 25-30 young people and 25-30 carers per arm (~120 interviews) to explore intervention acceptability. Participants recruited in the internal pilot phase (max n=10-12) will additionally be asked about their experiences of trial recruitment and research processes.

Eligible participants will be the cohort of participants who consented at trial recruitment/baseline to be contacted about an interview, as recorded on the YTU database. We will purposefully sample across sites, and intervention engagement levels (<4, 4+ sessions), and use maximum variation sampling to ensure a spread of participants in terms of age, gender, SES and baseline depression severity.

The final sample sizes for the young people and carer samples will be determined by data saturation; we will continue to recruit until team consensus suggests saturation has been achieved. Participants may include but not depend upon, recruiting young people-carer dyads.

# **Professionals:**

During the internal pilot, at the end of training, we will seek to interview all consenting professionals (therapists and supervisors) who have been trained in Behavioural Activation) to discuss their experiences and views of intervention training processes, perceived barriers/enablers to treatment delivery and service readiness.

During the main trial, we will invite all participating therapists and supervisors/service managers (approximately 12 per group) to have an interview. These interviews will explore post-treatment views on intervention preparation, delivery and implementation.

The final sample size of professionals for the embedded qualitative study will be determined by convenience in the absence of reaching saturation.

# 10.3. Recruitment

# Young person and carer recruitment

At the baseline visit, young people and carers will indicate in their consent/assent form whether they would be happy to be contacted about taking part in an interview with a member of the research team, 0-4 weeks after their 6-month follow-up date.

Consent to contact will be recorded on the YTU trial database. The research team will purposively select a sample across trial arms, sites and intervention engagement level (0, <4, 4+ sessions) and representing different ages, genders, socio-economic backgrounds and levels of depression to approach to participate.

Immediately after participants' 6-month follow-up date, a qualitative researcher from the research team will provide participants with a qualitative interview information sheet and invite a young people and/or their carers (where appropriate) to an interview. Participants will have at least 24 hours to decide whether to take part in the interview after receiving the information. After this point, a researcher will re-contact the participants to discuss any questions, complete an additional consent/assent form and arrange the interview. Interviews will be conducted within 4-6 weeks post primary outcome point in both internal pilot and main trial phase.

#### Professional recruitment

In the internal pilot phase, all professionals (BAY therapists and their supervisors from each site) who have been trained in BA will be invited to qualitative interviews to discuss the training that they received.

Additionally, all professionals (therapists and supervisors/service managers) as part of the RCT will be invited to attend an individual interview with a member of the research team to discuss their experiences and/or thoughts of treatment delivery. We will also invite any participating professionals who left the study early to attend an interview within 9 months of their last participation in the BAY Trial. Professionals will be provided with an information sheet outlining the aims of the interview and what participation will entail. Those interested in taking part will be asked to complete a consent form.

#### 10.4. Procedure

All interviews will be held online using a video conferencing platform approved by the study sponsor or via telephone and recorded via inbuilt recording software within the videoconferencing platform used or using an encrypted Dictaphone... In exceptional cases where remote interviews cannot be facilitated, on participant preference, they will be held in-person in a mutually convenient private location.

Interviews recorded on MS teams will be stored on Microsoft Office 365 cloud and subsequently downloaded and saved in a folder on the secure network on an NHS or University computer with access restricted to the study team. Recordings will be deleted from Microsoft Office 365 once downloaded. Participants will be given the option to switch their camera off so only an audio recording will be made.

Interviews recorded on Zoom will be audio recorded only and will be saved directly in a folder on the secure network on an NHS or University computer with access restricted to the study team. Interviews recorded on an encrypted Dictaphone will be securely transferred to a secure folder on the secure network on an NHS or University computer,

and will be deleted from the Dictaphone. Access to recordings will be restricted to the study team.

Topic guides for YP and parents will be co-developed with the PPI panel members' feedback to ensure the questions are appropriate and suitable for the participants.

All interviews will last 60-90 minutes and will be audio recorded and transcribed verbatim, to which participants would have given permission when signing the assent/consent form. Participants will be reminded that the discussion will be recorded before it starts. All recordings will be transcribed by a sponsor approved transcription company. When the transcriptions have been checked for accuracy by the research team, all audio-recordings will be erased. Interview transcripts will each be given an individual linking identifier to maintain participant confidentiality.

Interview schedules for parents and YP will be codeveloped with the PPI panel members and informed by the Theoretical Framework for Intervention Acceptability (TFA; Sekhon, Cartwright and Francis, 2017) Professional interviews will be informed by the TFA and the Consolidated Framework for Implementation Research (CFIR; Damschroder et al., 2009)

# 10.5. Data analysis

Interviews will be digitally recorded with consent and transcribed. We will use Framework Analysis, combining inductive and deductive coding by the constant-comparison method. Deductive codes will be informed by the Theoretical Framework for Intervention Acceptability (TFA; Sekhon, Cartwright and Frances, 2017) and Consolidated Framework for Implementation Research (CFIR; Damschroder et al., 2009). Each dataset will be analysed separately and combined in a data synthesis. Analysis will be led by a qualitative researcher, together with the YP co-researcher (for YP data) under the supervision of PB. Data interpretation will be discussed regularly, and a shared coding scheme agreed. New codes will be added, and duplicate or superfluous codes removed as analysis progresses. Excerpts of data analysis and preliminary study interpretations will be fed back to the project's PPI advisory panels and the research team for verification.

# 10.6. Ethical considerations

Confidentiality of participants and the data obtained during interviews will be maintained throughout. All interview transcripts will be assigned an identifier with no personal information and pseudonyms will be used when reporting all results. Personal information will be collected in the trial and linked to describe the sample. All recordings will be made using encrypted devices with recordings deleted immediately following transcription. A trained researcher will conduct all interviews and will have a relevant educational background and DBS check.

#### 11. ECONOMIC EVALUATION & MODELLING

The health economic analyses will be conducted following intention-to-treat principles and will follow a pre-specified health economics analysis plan (HEAP). All costs will be presented in Pound Sterling in a single cost year.

# 11.1 Cost-Utility & Cost-Effectiveness: trial-based analysis

The cost to train the BAY therapists and the cost of their time to deliver the intervention therapy sessions will be estimated as the intervention cost. This will be added to the cost of health and social care resources used by YP in the intervention arm to generate an overall cost for that treatment group. For the TAU+PE group, their overall cost will be generated from their use of health and social resources only. The primary analysis will take the health and social care perspective and so will only include these costs. A secondary analysis will include the cost of 'lost productivity' for parents/carers during the time they spend with YP at (and travelling to) healthcare contacts. Unit costs will be derived from published sources (e.g. NHS Schedule of Reference Costs; PSSRU Unit Costs of Health and Social Care) using the most up-to-date versions at the time of the analysis.

The measure of health benefit in the primary analysis will be YP's QALYs derived from the CHU-9D at baseline and 6-month follow-up. A secondary analysis will derive YP's QALYs from the EQ-5D-Y at these timepoints. QALYs will be estimated using an area under the curve approach.

The difference in costs between the treatment groups will be calculated using a glm regression model with log link and gamma family to account for the typically skewed nature of cost data. The difference in QALYs between the groups will be estimated using a linear regression model. Both regression models will include key covariates, as specified in the statistical analysis. An incremental cost-effectiveness ratio (ICER) will be calculated by dividing the difference in costs by the difference in QALYs between the treatment groups. This will be reported as a cost per QALY. Non-parametric bootstrapping will be used to produce a cost-effectiveness plane to demonstrate uncertainty in the results. A cost-effectiveness acceptability curve (CEAC) will also be generated to illustrate the probability that either treatment is cost-effective at a range of willingness to pay (WTP) thresholds.

The health utility of parents/carers during the study period will be derived from the EQ-5D-5L and compared between the treatment groups.

The time horizon for the primary analysis will be 6 months. An exploratory analysis over 12 months will also be conducted. As the study period does not extend beyond 12 months, no discounting will be applied to costs or health benefits.

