#### 3.3. Quantitative Outcomes

Measures will be administered to participants by a trained researcher at baseline (n=446), 12 weeks (n=446), 6 months (primary outcome, n=446), and 12 months post-randomisation (naturalistic follow up, n= approx. 300/participants recruited  $\geq 12$  months before trial end date). All measures and their time-points of completion are presented in Table 1.

 Table 1: Summary of assessments

			TIMELINE				
Assessment	Source	Method of Completion	Screening	Baseline	12 Weeks	6 Months	12 Months *
			PARTICIPANT- YOU	NG PERSON			
Screening	Screening Log	Research Assistant (RA) /Site staff	X				
Mood and Feelings Questionnaire (MFQ-C)	Questionnaire	Self-completion	X	Х	Х	Х	X
Contact Details	CRF	Research Assistant/Participant		X	YTU to be notified of changes to contact details		itact details
Demographics	CRF	Self-completion/RA assistance if requested		X			
Eligibility (including Inclusion and Exclusion Criteria)	CRF	PI/Research Assistant/PIs Delegate at site		Х			
Consent	Paper/Online Consent Form/REDCap	Self-completion / Research Assistant		Х			
Strengths & Difficulties Questionnaire (SDQ)	Questionnaire	Self-completion/RA assistance if requested		X	Х	Х	X
Development and Well- Being Assessment (DAWBA)	Online	RA led alongside participant if requested		X			
Revised Children's Anxiety and Depression Scale (RCADS) Brief Version	Questionnaire	Self-completion/RA assistance if requested		Х	Х	Х	Х

Behavioural Activation for Depression (BADS)	Questionnaire	Self-completion/RA assistance if requested		X	Х	X	X				
Self- harm & suicidality questions	CRF	Self-completion/RA assistance if requested		Х	Х	Х	Х				
Goal based outcomes	CRF	Self-completion/RA assistance if requested		X	X	Х	X				
Child Health Utility -9 Dimensions (CHU-9)	Questionnaire	Self-completion/ RA assistance if requested		Х	Х	Х	X				
EQ-5D-Y	Questionnaire	Self-completion/RA assistance if requested		X		Х					
Healthcare Service Use schedule	CRF	Self-completion (with assistance from carer)		X	X	Х	X				
Aspects of Care Contamination Checklist	CRF	Self-completion/RA assistance if requested			X	Х	X				
Working Alliance Inventory (WAI-S)	Questionnaire	Self-completion	(Collected halfway through intervention delivery)								
End of BA treatment Questionnaire	Questionnaire	Self-completion	(Collected after final session of BA therapy)								
Optional Qualitative Interview	Semi-structured interview	Interview				X					
			PARENT/CA	RER							

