# Child Health Utility-9 Dimensions (CHU-9D)

We will use the CHU-9D (Stevens, 2010) to derive health utility and calculate quality-adjusted life years (QALYs). The questionnaire consists of 9 domains, each with 5 statements (scored 1–5) that will assess the young person's functioning across domains of worry, sadness, pain, tiredness, annoyance, school, sleep, daily routine and activities on that specific day. For example: 1= I don't feel sad today, 2=I feel a little bit sad today, 3=I feel a bit sad today, 4=I feel quite sad today, 5=I feel very sad today. The responses under the 9 domains can be taken together as a description of the young person's "health state" using a descriptive system that combines all responses across all items (e.g. 11232152). Different utility weights were assigned to each level of each domain. Different combinations of responses across the 9 dimensions therefore result in different health states that have a utility value on a 0–1 scale, where 1 is perfect health and 0 is equivalent to being dead. The UK young people valuation set will be used to derive the utility values (Stevens, 2012). Utility values from each time point in the trial will be used to calculate quality-adjusted life years (QALYs) which will be the measure of health benefit in the economic evaluation.

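### Section 11.1 builds the primary 6-month QALYs from two CHU-9D values, while the CHU-9D section calls for every time point and Table 1 collects a 12-week value

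*Protocol*

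**What the plan says.** Section 11.1 takes the young person's "QALYs derived from the CHU-9D at baseline and 6-month follow-up" as the health benefit in the primary economic analysis. It continues "A secondary analysis will derive YP's QALYs from the EQ-5D-Y at these timepoints" and adds "QALYs will be estimated using an area under the curve approach". The horizon is given separately at the end of the same section: "The time horizon for the primary analysis will be 6 months". An exploratory 12-month analysis is also planned.

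The CHU-9D description in section 3.3.1 says something different: "Utility values from each time point in the trial will be used to calculate quality-adjusted life years". It presents these QALYs as the benefit measure of the economic evaluation.

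Table 1 (section 3.3) schedules the CHU-9D at baseline, 12 weeks, 6 months and 12 months. It schedules the EQ-5D-Y at baseline and 6 months only.

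**The concern.** The protocol gives two different rules for the same primary quantity. One uses the 12-week utility and the other does not. With two points, the area under the curve assumes that utility moves in a straight line over the whole 26 weeks, although an observation near the middle of that period is collected from all participants.

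Cost-effectiveness is part of the primary objective (section 3.1.1). The QALY difference is the denominator of the ICER and feeds the cost-effectiveness plane and the acceptability curve. Section 11.2 makes the long-term model conditional on evidence of cost-effectiveness within the study period, so the choice also bears on whether that model is built. If both rules stand and they give different ICERs, the choice could be made after the results are known.

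**Working it through.** **Do the sections really conflict?** Section 11.1 might be read as stating only a 6-month horizon. That does not fit the text. The horizon has its own sentence, and the same two time points are carried over to the EQ-5D-Y, which Table 1 collects only at those two visits. Section 11.1 therefore means a two-point calculation, and the CHU-9D description means one that includes 12 weeks.

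**Inputs.** Visits at 0, 12 and 26 weeks, that is 0, 12/52 and 26/52 years (section 3.3, taking 6 months as 26 weeks). Method: area under the curve (section 11.1), taken here as the trapezoid rule. Let d12 and d6 be the between-arm utility differences at 12 weeks and 6 months, with no difference at baseline. The protocol gives no utility, QALY or ICER figure, so there is nothing to reproduce, and every value of d12 and d6 below is assumed.

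**Formulas.**

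- Two points: 0.5 × (26/52) × d6 = 0.25 × d6.
- Three points: 0.5 × (12/52) × d12 + 0.5 × (14/52) × (d12 + d6) = 0.25 × d12 + 0.1346 × d6.
- Two-point minus three-point: 0.25 × [(12/26) × d6 − d12].

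The difference is zero only when d12 = (12/26) × d6, about 46% of the 6-month difference. This includes the case where both are zero. In the three-point area the 12-week visit has weight 0.25 and the 6-month visit 0.1346, so the value left out would carry the larger weight.

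**Illustrations (assumed differences).** The last column is the two-point ICER divided by the three-point ICER, holding the cost difference fixed.

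| d12 | d6 | Two-point | Three-point | Two-point relative to three-point | ICER ratio |
|---|---|---|---|---|---|
| 0 | 0.05 | 0.0125 | 0.0067 | +86% | 0.54 |
| 0.0231 | 0.05 | 0.0125 | 0.0125 | 0% | 1.00 |
| 0.025 | 0.05 | 0.0125 | 0.0130 | −4% | 1.04 |
| 0.05 | 0.05 | 0.0125 | 0.0192 | −35% | 1.54 |
| 0.05 | 0.025 | 0.0063 | 0.0159 | −61% | 2.54 |
| 0.05 | 0 | 0 | 0.0125 | −100% | undefined |

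For the fourth row: 0.25 × 0.05 = 0.0125; 0.25 × 0.05 + 0.1346 × 0.05 = 0.0192; 0.0192 / 0.0125 = 1.54.

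An early or fading effect makes the two-point gain smaller than the three-point gain, and a late effect makes it larger. Near-linear growth leaves the two almost equal.

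**The case against.** A reader might infer that the two-point method is biased against behavioural activation, because an eight-session treatment should show most of its effect by 12 weeks while usual care may begin with a wait. The protocol makes that path plausible, since section 8.2 allows usual care to be no intervention on a waiting list. It does not show it. There are no utility data, the readable text of section 8 gives no session interval or completion deadline, and the primary endpoint is at 6 months. Early, linear and late paths all remain open, so neither direction nor size can be claimed.

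Nor are the percentages measured errors. The three-point area also interpolates linearly, over 12 and 14 weeks, so the table compares two approximations. Using the extra observation is normally better, but it is not the truth. The ICER ratios also presume a positive ICER.

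It would likewise go too far to say that the final analysis will discard the 12-week value. Section 11 refers to a separate health economics analysis plan, which is not at hand and may settle the time points. That would not remove the conflict within the protocol.

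The most practical objection concerns missing data. Section 11 names no missing-data method for QALYs; the missing-at-random assumption and its sensitivity analyses in section 9.2 belong to the clinical outcome models. Section 9.1 plans for 70% retention, about 156 of 223 per arm. In a complete-case analysis, requiring a third value can only reduce the number analysed, and it recovers nobody who misses 6 months. This objection stands, and the fix has to deal with it.

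Finally, the MFQ-C primary outcome, the sample size and safety are unaffected, and the 12-week data are collected either way. That bears on how serious the point is, not on whether it holds.

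**Conclusion.** The inconsistency is established by the text: section 11.1 uses two CHU-9D values, while the CHU-9D description, together with Table 1, implies three within the 6-month horizon. The consequence is conditional. The two-point area departs from the three-point area unless the between-arm difference develops linearly from baseline. With assumed differences of 0.05 at both visits the gain is 35% lower and the ICER about 1.5 times as large at a fixed cost difference; other assumed paths give no change or the opposite sign. These figures rest on the trapezoid rule, no baseline difference and invented utility differences, and show only that the choice can matter. The point should be fixed before any unblinded economic analysis. It does not threaten the clinical conclusions of the trial.

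**What to change.** Amend section 11.1 so that primary QALYs over 6 months are the area under the curve from the CHU-9D at baseline, 12 weeks and 6 months, with the 12-month value added for the exploratory 12-month analysis. Keep the two-point calculation for the EQ-5D-Y, which is not collected at 12 weeks. A two-point CHU-9D analysis can be kept as a sensitivity analysis if a like-for-like comparison with the EQ-5D-Y is wanted. The CHU-9D description then needs no change.

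Carry the same wording into the health economics analysis plan and state there how missing 12-week utilities are handled, for example by multiple imputation, so that participants with baseline and 6-month values are not lost. Under imputation the 12-week value can also inform the 6-month value of those who miss that visit.

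The cost is one sentence in the protocol and a short addition to the economics plan, with no new data collection. The drawback is one more value that can be missing, hence the need to fix its handling in advance.
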